5.2.2 Secondary Endpoints

Secondary endpoints assessed through 6-months (unless noted otherwise) for the study are as follows:

- Secondary Safety Endpoint: Serious Adverse Event Rate within 3 and 6 Months

Defined as the Serious Adverse Event (SAE) rate involving the AV access circuit through 3 months and 6 months post-procedure.

- Access Circuit Primary Patency through 3 Months and 6 Months Post-Procedure
Defined as freedom from re-intervention in the access circuit or access circuit thrombosis through 3 months and 6 months post-procedure.
- Target Lesion Primary Patency through 3 Months and 6 Months Post- Procedure
Defined as freedom from CD-TLR or access thrombosis occurring in the target lesion through 3 months and 6 months post-procedure.
- Cumulative Target Lesion Reinterventions Measured through 3 Months and 6 Months Post-Procedure
Defined as proportion of subjects with TLR through 3 months and 6 months post-procedure.
- Number of Interventions Required to Maintain Target Lesion Patency through 3 Months and 6 Months Post-Procedure
Defined as number of TLR through 3 months and 6 months post-procedure.
- Number of Interventions Required to Maintain Access Circuit Patency through 3 Months and 6 Months Post-Procedure
Defined as number of reinterventions in the target lesion and/or access circuit through 3 months and 6 months post-procedure.
- Cumulative Access Circuit Thromboses Measured through 3 Months and 6 months Post-procedure.
Defined as proportion of subjects with access circuit thrombosis through 3 months and 6 months post-procedure.
- **Device Success:** Defined as successful delivery, treatment, and retrieval of the FLEX Vessel Prep device at index procedure.
- **Procedural Success:** Defined as maintenance of patency ($\leq 30\%$ residual stenosis) in the absence of peri-procedural Serious Adverse Event (SAE).
- **Clinical Success:** Defined as resumption of successful dialysis for at least one session after index procedure.
- **Balloon opening pressure** Defined as minimum inflation pressure required to efface target lesion noting parallel balloon walls.
- **Maximum balloon pressure** of angioplasty balloon(s) required during the interventional procedure to treat target lesion.
- **Patient Reported Pain** During the interventional procedure reported via Numerical Rating Scale (NRS).

6 Study Design

This is a prospective, multi- center, randomized (1:1) clinical study evaluating the FLEX Vessel Prep System followed with PTA (TEST arm) vs PTA alone (CONTROL arm) for the treatment of *de novo* or non-stented restenotic obstructive lesions up to 100 mm in length located in the arteriovenous dialysis fistulae in an upper extremity. Enrollment will continue until complete data sets are collected for up to 75 subjects from up to 7 sites in the US.

Once enrolled, subjects will remain in the study through completion of the required follow-up duration unless the subject withdraws consent, the subject expires, the investigator withdraws the subject, or VentureMed terminates the study for any reason. The enrollment phase is expected to take 3 months. The follow-up duration for each subject is up to 6 months. The total expected duration of the study is approximately 9 months.

7 Product Description

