14.7	SUSPENSION OR EARLY TERMINATION	26
15	REFERENCES	26

2 Definitions

Term	Definition
Access Circuit	The area from the AV access fistula arterial anastomosis to the axillosubclavian junction.
Access Thrombosis	A total occlusion within the AV access circuit due to thrombus formation which is rapidly evolving as confirmed by sudden onset of symptoms and documented by duplex ultrasound and/or angiography.
Arteriovenous "Dialysis" Fistulae (AVF)	The joining of an artery and vein for the purpose of hemodialysis access.
Clinical Success	Resumption of successful dialysis for at least one session after index procedure.
De Novo Lesion	A lesion that has not been previously treated.
Device Success	Successful delivery, treatment, and retrieval of the FLEX Vessel Prep System or the control device at index procedure.
Dissection Types A-F	
Intimal disruption of the vessel wall with or without medial or adventitial contrast staining, classified as per the NHLBI (National Heart, Lung, and Blood Institute) criteria as follows:
 
A) Luminal Haziness: Minor radiolucent areas in the lumen without impairment of flow or persistent dye staining after contrast runoff.
 
B) Linear Dissection: Luminal flap that is radiolucent and that runs parallel to the vessel wall with contrast injection but without impairment of flow or persistent dye staining after contrast runoff.
 
C) Extraluminal Contrast (i.e., "cap dissection"): Contrast appears outside of the vessel lumen as an "extraluminal cap." The staining appears even after contrast clears the lumen.
 
D) Spiral Dissection: Spiral radiolucent luminal filling defects; often persistent staining after contrast clears from the vessel.
 
E) Dissection with Reduced Flow: New and persistent filling defects in the vessel lumen
 
F) Dissection with Total Occlusion: Lesions that progress to

Term	Definition
	impaired flow or total occlusion
Embolism	The obstruction of a blood vessel by a foreign substance or a blood clot that travels through the bloodstream, lodging in a blood vessel or plugging the vessel.
Enrollment	The time the guidewire has successfully crossed the lesion to be treated.
Optimal PTA	Repeated and prolonged balloon inflations aimed to achieve <50% residual stenosis (visual estimate) without stenting.

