5.2 Endpoints

5.2.1 Primary Endpoints

Primary endpoints for the study are as follows:

- Primary Efficacy Endpoint: Target Lesion Primary Patency Rate through 6 Months

Defined as freedom from clinically driven target lesion re-intervention (CD-TLR) or access circuit thrombosis measured through 6 months post-procedure.

- Primary Safety Endpoint: Serious Adverse Event Rate within 30 Days

Defined as the Serious Adverse Event (SAE) rate involving the AV access circuit through 30 days post-procedure.

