8.2 Inclusion Criteria

1. Patient is ≥21 years of age.
2. Patient has a life expectancy of ≥12 months.
3. Patient has a native AV fistula created ≥ 60 days prior to the index procedure.

4. The target AV fistula has undergone successful dialysis for at least 8 of 12 sessions during a four-week period.
5. Patient has a *de novo* and/or non-stented restenotic lesion located between approximately 2 cm proximal to the arteriovenous anastomosis and axillosubclavian junction with $\geq 50\%$ stenosis.

Note: If the lesion is located in the cephalic arch, the treatment may be delivered up to 2 cm into the subclavian vein.

6. Patient has a target lesion (which may include a tandem lesion) that is ≤ 100 mm in length (by visual estimate).

Note: Tandem lesions may be enrolled provided they meet all of the following criteria:

- Separated by a gap of ≤ 30 mm (3 cm).
- Total combined lesion length, including 30 mm gap, ≤ 100 mm.
- Able to be treated as a single lesion.

7. Patient has a target vessel diameter of 4.0 – 12.0 mm (by visual estimate)
8. Patient underwent successful crossing of the target lesion with the guidewire.
9. Patient provides written informed consent prior to enrollment in the study.
10. Patient is willing to comply with all follow-up evaluations at specified times.

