8.3 Exclusion Criteria

1. Patient is pregnant or breastfeeding.
2. Patient is receiving immunosuppressive therapy.
3. Patient has undergone prior intervention of access site within 30 days of index procedure.
4. Patient with anticipated conversion to peritoneal dialysis.
5. Patient has an infected AV access or systemic infection.
6. Patient has planned surgical revision of access site.
7. Patient with secondary non-target lesion requiring treatment within 30 days post index procedure.
8. Patient with hemodynamically significant central venous stenoses that cannot be successfully treated prior to treatment of the target lesion.
9. Patient with target AVF or access circuit which previously had thrombectomy within last 30 days.
10. Patients judged to have a lesion that prevents complete inflation of an angioplasty balloon or proper placement of the delivery system.
11. Patient with target lesion located central to the axillosubclavian junction.
12. Patient has significant arterial inflow lesion requiring treatment more than 2 cm upstream from the anastomosis in the AV access.
13. Patient has presence of pseudoaneurysm or aneurysm requiring surgical revision at the target lesion site.
14. Patient with known contraindication, including allergic reaction, or sensitivity to contrast material that cannot be adequately pre-treated.

15. Patient who cannot receive recommended antiplatelet and/or anticoagulant therapy.
16. Patient with clinically significant Steal Syndrome requiring treatment.
17. Patient is enrolled in another investigational drug, device, or biologic study and has not completed the primary endpoint or was previously enrolled in this study.
18. Patient has a co-morbid condition that, in the judgment of the Investigator, may cause him/her to be non-compliant with the protocol or confound the data interpretation.
19. Patient has AV fistula created via endovascular technique.

9 Study Procedures

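### Do two 6-month rates named Target Lesion Primary Patency, and an access circuit that stops at the anastomosis, leave the endpoints unsound?

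*Combined protocol and SAP*

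**What the plan says.** Section 5.2.1 names Target Lesion Primary Patency Rate through 6 Months as the primary efficacy endpoint, with this definition: "Defined as freedom from clinically driven target lesion re-intervention (CD-TLR) or access circuit thrombosis measured through 6 months post-procedure". Section 5.2.2 gives the secondary, Target Lesion Primary Patency through 3 and 6 months, with a different one: "Defined as freedom from CD-TLR or access thrombosis occurring in the target lesion through 3 months and 6 months post-procedure". The synopsis in Section 3 repeats both rules, so the difference is not confined to one place.

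Section 2 defines the Access Circuit as "The area from the AV access fistula arterial anastomosis to the axillosubclavian junction" and Access Thrombosis as "A total occlusion within the AV access circuit due to thrombus formation". Inclusion criterion 5 (Section 8.2) admits a "lesion located between approximately 2 cm proximal to the arteriovenous anastomosis and axillosubclavian junction". For cephalic arch lesions it adds that "the treatment may be delivered up to 2 cm into the subclavian vein". Exclusion 12 (Section 8.3) removes the case "Patient has significant arterial inflow lesion requiring treatment more than 2 cm upstream from the anastomosis in the AV access", and exclusion 11 removes the case "Patient with target lesion located central to the axillosubclavian junction".

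Under Section 12, a 6-month proportion has as its denominator the subjects with an event plus those followed for at least 150 days. Section 9.7 withdraws a subject whose access is abandoned.

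**The concern.** Two 6-month results could be reported under one name with different thrombosis rules, and the narrower rule can never give the lower rate. Someone quoting a target lesion patency figure without its label could pick either. The 3-month rate exists only under the narrower rule, so it might be paired wrongly with the primary 6-month rate.

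The boundary raises a second worry. If a target lesion lies just upstream of the anastomosis, it is outside the circuit as defined. Read literally, a thrombosis confined to it is not an access thrombosis under either rule. A re-intervention there would not end access circuit primary patency, yet it would be counted among the interventions needed to maintain that patency. It would also be unclear whether a serious adverse event there enters the primary safety rate, which is limited to events involving the circuit.

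**Working it through.** **Naming: which way the two rules differ.** For one arm, let *a* be subjects with CD-TLR or target-lesion thrombosis, *b* those whose only event is a circuit thrombosis elsewhere, *b1* the part of *b* followed at least 150 days, and *c* event-free subjects followed at least 150 days. Under Section 12:

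- primary patency = c / (a + b + c)
- secondary patency = (c + b1) / (a + b1 + c)

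The second is never below the first. The two rules disagree only on the subjects in *b*.

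**Size.** Inputs: up to 75 subjects randomized 1:1 (Sections 3 and 6), taken as 37 control and 38 test; planning rates of 60% and 80% (Section 12), taken as 22/37 and 30/38. The value b = 2 is an assumption. It gives a = 13 in control and a = 6 in test.

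| Case | Control | Test | Difference (points) |
|---|---|---|---|
| Primary rule | 22/37 = 59.5% | 30/38 = 78.9% | 19.5 |
| Secondary, b = 2 in each arm, all followed 150 days | 24/37 = 64.9% | 32/38 = 84.2% | 19.3 |
| Secondary, b = 2 in each arm, all withdrawn earlier | 22/35 = 62.9% | 30/36 = 83.3% | 20.5 |
| Secondary, b = 2 in control only | 64.9% or 62.9% | 78.9% | 14.1 or 16.1 |
| Secondary, b = 2 in test only | 59.5% | 84.2% or 83.3% | 24.8 or 23.9 |

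Differences use unrounded rates. In the last two rows the first figure is for subjects followed 150 days and the second for those withdrawn earlier. One subject is worth 1/37 = 2.7 or 1/38 = 2.6 points, or 1/25 = 4.0 points if only 25 per arm were evaluable (assumed).

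**Yardstick.** Section 12 states a half-width of about 25 points for efficacy. The simple Wald formula gives 1.96 × √(0.6×0.4/37 + 0.8×0.2/38) = 20.3 points, and it reaches 24.8 at 25 per arm. The plan states neither the method nor the evaluable number. The largest shift in the table is 19.5 − 14.1 = 5.4 points, which is small against either width.

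**Boundary: each type of event at the arterial edge.**

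- *Re-intervention on the target lesion.* Section 2 ties TLR to the treated lesion, not to the circuit. If clinically driven, it fails both target lesion endpoints. The count of interventions for the circuit names the target lesion explicitly, so it is included there too. Only access circuit primary patency misses it on a literal reading.
- *Thrombosis confined to the edge and re-opened.* Section 2 lists thrombolysis, angioplasty and stenting as TLR and treats stenosis of 70% or more as clinically driven with or without dysfunction. A re-opened total occlusion therefore fails both target lesion endpoints.
- *Thrombosis confined to the edge and never re-opened.* On a literal reading this escapes the thrombosis component. It needs an occlusion of a target lesion lying wholly in about 2 cm of artery, with no re-opening.
- *Serious adverse event.* The safety endpoint covers events involving the circuit, which is broader than events within it. As an illustration, one event classified the other way moves 2/38 = 5.3% to 1/38 = 2.6%, against a stated half-width of about 17 points.

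**Venous end.** Exclusion 11 keeps target lesions out of the zone beyond the junction, so only the treatment extension of up to 2 cm lies there. A re-intervention confined to that extension is not clearly a TLR, because TLR refers to the lesion. This too is a narrow matter of classification.

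**The case for a change.** The strongest argument for acting is that Section 12 presents this as an estimation study, and an estimate is only as good as its definition. Saying that significance is not expected does not excuse two definitions under one name, and a new name for the secondary would cost almost nothing. The literal inconsistency at the arterial edge is also genuine: the intervention count and access circuit patency can disagree about the same procedure.

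The textual differences stand, but they do not lead to a change. Each definition is printed with its endpoint, and the primary or secondary label separates them. The secondary's 3- and 6-month rates follow one rule, and a primary endpoint defined at 6 months need not have a 3-month counterpart. The proportion with access circuit thrombosis is a separate secondary endpoint at 3 and 6 months, so a reader can see an upper limit on how many subjects the two rules could classify differently. The gap between the two rates is the gap between a circuit-wide and a lesion-specific question, and both are reasonable to ask.

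For the boundary, the remedy is less innocent than the problem. Extending the circuit for endpoint purposes changes the thrombosis component of primary efficacy and the scope of primary safety, although enrollment was completed in April 2022 (Section 3). Extending it to everything treated at the index procedure could also draw in central veins, since exclusion 8 contemplates central stenoses being treated first. Re-sorting events across a 2 cm line needs location data that the documents do not show to be recorded.

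**Conclusion.** No change follows. The shared name is a labelling matter: both rates are well defined, the direction of any difference is known, and renaming one would alter no result. Under the assumed two discordant subjects per arm, the difference between arms stays within 19.3 to 20.5 points. With both in one arm it runs from 14.1 to 24.8, which matters only if one rate is mistaken for the other.

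The boundary mismatch is a gap that analysts would fill sensibly, by treating an event at the target lesion as an event of the access it serves. Re-opened lesions already count in the primary efficacy endpoint. The residue is an arterial-edge occlusion never re-opened, the literal reading of access circuit primary patency, and borderline safety events.

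This rests on three things. The documents give no frequency for non-target thrombosis or edge-zone lesions, so the sizes above are illustrations. The word proximal in inclusion 5 is read as the arterial side, which exclusion 12 supports. Section 12 also refers to a Statistical Analysis Plan for further detail; no separate text on these definitions was available for this check, and it may already settle both points.

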7.1 FLEX Vessel Prep™

The FLEX Vessel Prep System™ is an over-the-wire sheathed catheter with a three-strut treatment element near the distal tip. The Treatment Element consists of three independent flexible struts, each with a precision blade, mounted on the proximal end. As the device is pulled back in a retrograde fashion through the target lesion, the Treatment Element “flexes” providing continuous engagement along the lesion to create controlled depth microincisions.

7.2 PTA Balloon

The brand and type of PTA balloon(s) used will be at the discretion of the treating physician and used according to its IFU. PTA balloons consist of an over-the-wire catheter with a balloon fixed at the distal tip. Within the lesion the balloon is inflated to a pressure that allows full effacement. Standard pressure balloons (<20atm), high pressure (>20atm), and ultra-high pressure (>30atm) have been used for resistant AV stenosis.⁶ Balloon sizing matches reference vessel diameter (RVD) 1:1 and usually extends beyond the lesion length.

8 Selection of Subjects

8.1 Study Population

This study will enroll subjects with a *de novo* or non-stented restenotic obstructive lesions up to 100 mm in length, located in the native arteriovenous dialysis fistulae in the upper extremity.

8.2 Inclusion Criteria

1. Patient is ≥21 years of age.
2. Patient has a life expectancy of ≥12 months.
3. Patient has a native AV fistula created ≥ 60 days prior to the index procedure.

4. The target AV fistula has undergone successful dialysis for at least 8 of 12 sessions during a four-week period.
5. Patient has a *de novo* and/or non-stented restenotic lesion located between approximately 2 cm proximal to the arteriovenous anastomosis and axillosubclavian junction with $\geq 50\%$ stenosis.

Note: If the lesion is located in the cephalic arch, the treatment may be delivered up to 2 cm into the subclavian vein.

6. Patient has a target lesion (which may include a tandem lesion) that is ≤ 100 mm in length (by visual estimate).

Note: Tandem lesions may be enrolled provided they meet all of the following criteria:

- Separated by a gap of ≤ 30 mm (3 cm).
- Total combined lesion length, including 30 mm gap, ≤ 100 mm.
- Able to be treated as a single lesion.

7. Patient has a target vessel diameter of 4.0 – 12.0 mm (by visual estimate)
8. Patient underwent successful crossing of the target lesion with the guidewire.
9. Patient provides written informed consent prior to enrollment in the study.
10. Patient is willing to comply with all follow-up evaluations at specified times.

8.3 Exclusion Criteria

1. Patient is pregnant or breastfeeding.
2. Patient is receiving immunosuppressive therapy.
3. Patient has undergone prior intervention of access site within 30 days of index procedure.
4. Patient with anticipated conversion to peritoneal dialysis.
5. Patient has an infected AV access or systemic infection.
6. Patient has planned surgical revision of access site.
7. Patient with secondary non-target lesion requiring treatment within 30 days post index procedure.
8. Patient with hemodynamically significant central venous stenoses that cannot be successfully treated prior to treatment of the target lesion.
9. Patient with target AVF or access circuit which previously had thrombectomy within last 30 days.
10. Patients judged to have a lesion that prevents complete inflation of an angioplasty balloon or proper placement of the delivery system.
11. Patient with target lesion located central to the axillosubclavian junction.
12. Patient has significant arterial inflow lesion requiring treatment more than 2 cm upstream from the anastomosis in the AV access.
13. Patient has presence of pseudoaneurysm or aneurysm requiring surgical revision at the target lesion site.
14. Patient with known contraindication, including allergic reaction, or sensitivity to contrast material that cannot be adequately pre-treated.

15. Patient who cannot receive recommended antiplatelet and/or anticoagulant therapy.
16. Patient with clinically significant Steal Syndrome requiring treatment.
17. Patient is enrolled in another investigational drug, device, or biologic study and has not completed the primary endpoint or was previously enrolled in this study.
18. Patient has a co-morbid condition that, in the judgment of the Investigator, may cause him/her to be non-compliant with the protocol or confound the data interpretation.
19. Patient has AV fistula created via endovascular technique.

9 Study Procedures

9.1 Schedule of Events

Table1 provides an overview of the assessment requirements for the study.

Table 1: Study Assessment Requirements

Assessment/Procedure	Baseline/Screening (within 30 days of procedure)	Index Procedure	Discharge (within 7 days post-procedure)	30 Days (± 7 days)	3 Months (90 ± 15 days)	6 Months (180 ± 30 days)	Unscheduled Visit	Target AVF Abandonment
Informed Consent	X							
Medical History	X							
Physical Exam	X						X	
Medication Assessment	X	X	X					
Numeric Rating Scale	X	X						
Angiography		X					X*	
Randomization		X						
Serious Adverse Event Collection		X	X	X	X	X	X	X
Abandonment of Fistula								X

* Collect if revascularization required.

9.2 Subject Consent

All subjects must undergo the consent process, possess the mental capacity to provide Informed Consent, and sign the ICF prior to enrollment and prior to undergoing any assessments or procedures that are study-specific (defined as those that would not be conducted if the subject were not participating in the study).

The ICF and other written explanatory information will be revised if significant new information that may be relevant to the subject's consent becomes available, or there is an amendment to the protocol which necessitates a change to the ICF. The subjects should be re-consented in a timely manner and will be asked to confirm willingness to continue his/her participation in the study and obtain his/her signature (with printed name) on the revised consent form. All revisions to the consent form must be approved in advance by the IRB.

